5. METHODS

5.8 Statistical Analyses

Estimated attrition: Combining armodafinil non-responders and those who decline counseling, we estimate that 80% of patients starting armodafinil treatment will enter counseling. Patients who are self-described as fatigued but who do not meet fatigue criteria will enter counseling without a medication phase, so 100% of these patients should enter counseling.

Estimated effect magnitude of armodafinil plus BA-PEP: In prior trials of modafinil and armodafinil, 27% achieved a specific work or training goal without counseling. In our current study combining armodafinil and counseling, 62% randomized to BA achieved their goal of work or training and 20% of SC patients did so. We expect patients not meeting fatigue criteria to follow the same percentages. We thus conservatively anticipate response rates of 60% for BA patients vs. 25% for SC patients.

5.8.2 Data Management. All research ratings and self-report scales are checked for accuracy and completeness before the patient leaves the clinic, and omissions or inconsistencies addressed. The data are double entered into a PC-based data management system. Data are analyzed using PC-based statistical packages.

Sample size and randomization: We propose to enroll a total of 140 patients (100 who are fatigued, and 40 who self-described as fatigue but do not meet fatigue criteria) seeking treatment to return to work with counseling, and armodafinil for those patients who are fatigued. The randomization will be carried out by the statistician. Individuals will be stratified by fatigue (two levels: those who will be given armodafinil for fatigue, and those who will not be given armodafinil). Stratification will ensure comparable representation of fatigued and non-fatigued patients across the treatment groups. The randomization sequences will be balanced in blocks of random size (2, 4) to prevent clinicians from guessing what the next patient's treatment might be.

Note #1: We will review baseline sociodemographic, psychiatric, medical history variables, HCV infection and HIV illness stage to determine whether there are significant differences between treatment groups on any relevant measure. If so, each measure will be studied in terms of their relationship to treatment outcome. If related to outcome, they will be entered as covariates in all outcome analyses. To distinguish between depression and fatigue, a depression measure (BDI [67]) will be used as a covariate in all analyses. In addition to standard scoring, the depression measures (BDI and HAM-D [67]) will be adjusted and scores prorated to exclude the fatigue items.

Missing Data. The pattern and distribution of missing data will be examined, and recourse taken to assess randomness and correlates as described in Cohen and Cohen [87, Chapter 7]. Assuming it is randomly distributed, appropriate estimates of missing values will be generated and used in analyses. For AIM 2 the examination of the secondary outcomes across the treatment period (i.e. BADS and EROS Scales), we will be using Linear Mixed Models for analyses. In the presence of missing data, Mixed Models uses all data, estimates parameters and test hypotheses about them but do not impute missing values [88], and Mixed Models can reduce bias due to dropouts [89]. For dichotomous outcomes, secondary

analyses will be performed that use alternative methods of imputation (e.g. last observation brought forward).³

Attrition. We will deal with dropouts in 3 ways: excluding dropouts, counting dropouts as failures, and finally counting dropouts as responders, providing an idea of all possible outcomes are. As noted above, we will use Linear Mixed Models for analyses where appropriate, which can reduce bias due to dropouts.

Data Transformation. We will check all variables in terms of univariate and bivariate distributions to make sure any data analytic method we use appropriately reflects the relationship between the variables-- e.g. we will use nonlinear transformations and polynomial regression as necessary.

Definition of primary dependent variables:

Work: paid employment: 4+ hours/week including stipend jobs; volunteer work; Increased work hours: at least 20% increase with a minimum increase of 4 hours/week.

Training: Includes enrollment in GED classes, degree and vocational programs, computer classes, unpaid or stipend internships.

5.8.3: Analytic Strategies. (End points are final study visit and 3-month follow-up visit)

Specific Aim 1: to determine whether more patients in BA-PEP (N=70) return to work or start training compared to SC patients (N=70).

Hypothesis 1: Our primary outcome measure is success in work/training goal attainment using a modified GAS score; we hypothesize that 60% of BA-PEP patients will succeed as compared to 25% of SC patients. BA-PEP will significantly promote success in work goal attainment as compared to SC.

Analysis Plan: The effect of BA-PEP on the primary outcome (work goal attainment) will be examined using a logistic regression (PROC LOGISTIC in SAS[®]) adjusted for appropriate covariates (e.g., stratification variable, depression measure).

Specific Aim 2: Determine whether secondary outcomes, as measured from baseline to the end of treatment, differentiate between BA-PEP and SC. These include the Behavioral Activation Depression Scale, the Environmental Reward Observation Scale (EROS), Endicott Quality of Life, Role Function scale, and Mastery.

Hypothesis 2: Over time, the BA-PEP patients will show significantly more improvement compared to SC patients.

Analysis Plan: Hypothesis 2 will be analyzed using longitudinal mixed effect models (PROC GLIMMIX in SAS[®]) with main effect of time, treatment and interaction between treatment and time effect. The within subjects repeated measure across time will be the baseline session, session 4, and session 8 [end of treatment] assessments for the BADS Scales and the EROS, and the between subjects factor will be the two treatments (i.e. SC and BA-PEP counseling). Demographic measures and other characteristics that are significantly different between the two treatment groups at baseline, will be included as covariates. The main focus of the analysis will be on the interaction term of treatment and time, which addresses treatment group response over time. If the interaction term of treatment and time is found to be significant, we will test the contrast between treatment groups at session 8 [end of treatment].

Specific Aim 3: To identify predictors of success in goal attainment, including moderator variables such as concurrent Axis I depression, baseline BDI scores, health history and status, substance use history, time since last employed full-time and neuropsychological function. We will also examine mediating variables such as changes in apathy, mastery, coping style, motivation, mood (since starting counseling) and quality of life.

Hypothesis 3: We expect several of these characteristics particularly depression, age, health status and neuropsychological function, to show significant association to successful goal attainment.

Analysis Plan: We will use Logistic Regression (LR) Analysis available in SAS® statistics package (PROC LOGISTIC). This LR procedure will be performed hierarchically within each treatment arm separately, as well as the combined treatments (BA-PEP + SC treatments). The dichotomous dependent outcome measure will be successful goal attainment or not. At the first analysis step, age sex and education and possibly other covariates will be entered into the model, followed by the measures mentioned above using the backward stepping procedure. We will also examine moderator variables by investigating the interaction of treatment arm with each variable listed above. We will examine as mediator variables the changes in apathy, mastery, coping style, motivation, mood, and quality of life from baseline to session 4. Change in baseline to session 4 will be used in order to have a reliable measurement before or closest to obtaining the goal for those that will obtain the goal, since obtaining the goal could also affect these potential mediator variables.

Power Considerations (Power calculations do not include Historical Control data.)

Pilot Data: In our pilot work, we have treated 31 patients with the BA-PEP; 19 (61%) achieved their goals. In the combined modafinil and armodafinil RCTs, about 28% who wished to do so returned to work.

Hypothesis 1: 60% of BA-PEP treated patients will attain their goal compared to 25% of the SC treated patients. We will enroll 70 patients into each treatment arm (50 who responded to armodafinil and 20 who self-described as fatigued but did not meet fatigue criteria). With expected rates of 60% and 25% goal attainment, a difference of 35%, power is over 95%. Differences as small as 23% can be detected with 80% power, for reasonable percentages of goal attainment in the SC treated patients, e.g., (48% BA-PEP vs. 25% SC), (53% BA-PEP vs. 30% SC), (63% BA-PEP vs. 40% SC).

Hypothesis 2: We predict that the secondary assessments will distinguish between the two treatment groups with BA-PEP patients showing more improvement by the end of the treatment period compared to SC patients. Using power estimates for three repeated measures (baseline session, session 4, and session 8 [end of treatment]), for 70 patients per group, alpha set at $p < .05$ for a two-tailed test and correlation between repeated measures estimated at .30: (Effect size/Power) .45 [medium]/80%, .48/85%, .52 /90%, .58/95%.

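### The SAP implies two different randomised populations: 140 enrolled with some lost before counselling, and 140 already in arms whose fatigued members are armodafinil responders

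*SAP*

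**What the plan says.** Under Sample size and randomization (SAP 5.8.2) the intake is given as: "We propose to enroll a total of 140 patients (100 who are fatigued, and 40 who self-described as fatigue but do not meet fatigue criteria". The same paragraph sets the strata: "Individuals will be stratified by fatigue (two levels: those who will be given armodafinil for fatigue, and those who will not be given armodafinil". The Estimated attrition paragraph at the start of 5.8 combines non-responders with patients who decline: "we estimate that 80% of patients starting armodafinil treatment will enter counseling". Patients outside the medication stratum are all expected to enter counselling.

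Specific Aim 1 in 5.8.3 compares 70 BA-PEP patients with 70 SC patients. Under Power Considerations, Hypothesis 1, the arms are made up differently: "We will enroll 70 patients into each treatment arm (50 who responded to armodafinil and 20 who self-described as fatigued but did not meet fatigue". Power there is stated as over 95% for 60% vs 25%, and as 80% for differences of 23 points.

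The Attrition paragraph in 5.8.2 handles dropouts in three ways: "excluding dropouts, counting dropouts as failures, and finally counting dropouts as responders". It neither defines a dropout nor names one of the three as primary.

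**The concern.** The strata are labelled by who is going to receive the drug, and the 140 are enrolled patients. That reads as allocation before the medication phase. An arm containing 50 known responders can only be assembled after that phase. The two descriptions lead to different Aim 1 populations.

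If allocation comes first, some patients are assigned to BA-PEP or SC and leave before receiving any counselling. Their outcomes say nothing about which counselling works better. Keeping them in the comparison pulls the arms together, and removing them leaves fewer than 70 per arm. The plan's power figures allow for neither. A statistician holding only this SAP could not say who belongs in the primary analysis.

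**Working it through.** **Inputs.**
- From 5.8 and 5.8.2: 100 fatigued and 40 other patients enrolled; 80% of armodafinil starters and 100% of the others reach counselling; 27% reached a goal without counselling in prior trials.
- From 5.8.3: 70 per arm; "60% of BA-PEP treated patients will attain their goal compared to 25% of the SC treated patients"; further cases of 48 vs 25, 53 vs 30 and 63 vs 40.
- Assumed: two-sided 0.05, because "alpha set at $p < .05$ for a two-tailed test" is written for Hypothesis 2 only; loss before counselling equal in both arms.

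**Formula.** Two-proportion normal approximation with n per arm and p̄ the mean of p1 and p2:

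power = Φ{ [ |p1 − p2| − 1.96·√(2p̄(1 − p̄)/n) ] / √[ (p1(1 − p1) + p2(1 − p2))/n ] }

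**Step 1: the plan's own figures, n = 70.** For 60 vs 25: (0.35 − 0.1638)/0.0781 = 2.38, so power is 99.1%. For 48 vs 25: (0.23 − 0.1595)/0.0790 = 0.892, so 81.4%. For 53 vs 30 it is 79.5%, and for 63 vs 40 it is 78.3%. The stated figures are reproduced to within 2 points, but only with all 70 per arm at the full counselled rates.

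**Step 2: the counts.** 100 × 0.80 = 80 fatigued patients reach counselling, or 40 per arm. The power section has 50 responders per arm, or 100. Both cannot hold for the same 140 patients.

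**Step 3: allocation before armodafinil, everyone kept.** Per arm, 50 × 0.20 = 10 of 70 are never counselled. If q is their success rate, each arm's rate becomes p × 60/70 + q × 10/70. The q term cancels from the difference, so 35 × 60/70 = 30.0 points and 23 × 60/70 = 19.7 points whatever q is.

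| Rate assigned to the 10 | 60 vs 25 becomes | Power | 48 vs 25 becomes | Power |
|---|---|---|---|---|
| 0% (failures) | 51.4 vs 21.4 | 96.6% | 41.1 vs 21.4 | 71.5% |
| 27% (plan's no-counselling rate) | 55.3 vs 25.3 | 95.9% | 45.0 vs 25.3 | 68.9% |
| 100% (responders) | 65.7 vs 35.7 | 95.2% | 55.4 vs 35.7 | 65.2% |

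Restoring 80% power for the diluted 48 vs 25 case would need 86 per arm (failures) or 91 per arm (27%).

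**Step 4: only counselled patients analysed, 140 enrolled.** 80 + 40 = 120, or 60 per arm, without dilution. Power is 98.0% for 60 vs 25, and 75.1%, 73.0% and 71.8% for the three 23-point cases. The difference detectable with 80% power is 24.5 to 25.3 points.

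**Step 5: 140 randomised at counselling entry.** 100/0.80 = 125 patients must start armodafinil, and 125 + 40 = 165 must be enrolled. Only then do the stated power figures stand as written.

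**The case against.** The stratification sentence gives no time of allocation. Its future tense matches the rest of a plan written in that tense, and the next sentence simply calls the strata fatigued and non-fatigued. The remaining text leans towards allocation at counselling entry: the arms contain responders, the two treatments are forms of counselling, and the Aim 2 measurements run over counselling sessions. The time of randomisation may also be set in the protocol, so its absence from the SAP is no fault in itself. All of this stands. It does not remove the conflict, because a loose stratum label would still leave 80 against 100 fatigued patients.

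Three stronger readings are tempting and are not supported:
- A reader might infer that the SAP fixes allocation before the drug. It only implies this.
- A reader might infer that the Attrition paragraph sweeps never-counselled patients into its dropout rules. The term is undefined, and 5.8 describes these patients separately, as non-responders and decliners.
- A reader might infer that excluding them biases the comparison. That needs the arm to be known during the medication phase, so that it could affect the judgement of response or the acceptance of counselling. The SAP does not say that it is known. If it is not, excluding them costs numbers but does not dilute the contrast.

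**Conclusion.** The point holds as an inconsistency about who is randomised and analysed, not as proof that allocation precedes the drug. If allocation does come first and never-counselled patients are kept, the expected difference falls from 35 to 30 points.

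A reader might take this to undermine the main power claim. It does not: for 60% vs 25%, power stays at 95.2% to 96.6%, so the statement of over 95% survives. What is not delivered is 80% power for 23 points. For 48% vs 25% it is 65% to 72% with the diluted contrast. With 60 per arm undiluted, the three 23-point cases have 72% to 75%.

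These results assume a two-sided 0.05 test for Hypothesis 1, the plan's 80% estimate, equal loss in both arms, and an unadjusted two-proportion approximation in place of the planned adjusted logistic regression.

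**What to change.** Reconcile 5.8.2 with the power section of 5.8.3 by making these changes:

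1. State that randomisation, within stratum, takes place at counselling entry. For the medication stratum this is after response and acceptance of counselling have been recorded.
2. Define the Aim 1 analysis set as all patients randomised at that point.
3. Describe medication-phase losses separately and say that the three dropout rules do not apply to them.
4. State whether 140 counts patients enrolled or patients randomised. If enrolled, restate the power figures for about 60 per arm, as in Step 4. If randomised, state the intake of about 165 that this implies.

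The cost is SAP wording and a defined moment at which the statistician releases the allocation. No visits or procedures are added. With 140 enrolled, the downside is that about 120 are randomised and the detectable difference rises from 23 to about 25 points. Power for 48% vs 25% is then 75.1%, still below 80% but above the 65% to 72% of the diluted comparison.

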5.8.4. Additional Analyses (Examples)

1. The historical Control data will be added to all analyses described above.
2. Attainment of secondary goals (other than work/training): In addition to the simple dichotomous outcome for work/training, patients are asked to identify additional goals. We will analyze scores on the Goal Attainment Scale (GAS) which provides a more fine-grained description of progress made toward these other goals.

Analysis: We will use ANCOVA, first including only the highest ranked in priority, and then their combination, and any variables found to be unbalanced in the randomization or significantly predictive of outcome also will be used as covariates.

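### Covariates for the primary comparison are chosen by significance-testing randomized arms and then looking at outcome, so the Aim 1 model is not fixed in advance

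*SAP*

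**What the plan says.** Note #1, under SAP 5.8.2, sets a two-step rule. Baseline sociodemographic, psychiatric and medical-history variables, HCV infection and HIV stage are reviewed "to determine whether there are significant differences between treatment groups on any relevant measure". Measures that differ are then examined against treatment outcome: "If related to outcome, they will be entered as covariates in all outcome analyses". That scope includes Aim 1. The note gives no candidate list, no test, no significance level and no criterion for being related to outcome.

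One covariate is fixed: "a depression measure (BDI [67]) will be used as a covariate in all analyses". Two scorings are planned, however. Besides standard scoring, "the depression measures (BDI and HAM-D [67]) will be adjusted and scores prorated to exclude the fatigue items". The SAP does not say which version is the covariate.

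The Aim 1 analysis plan (5.8.3) describes the primary logistic regression as "adjusted for appropriate covariates (e.g., stratification variable, depression measure". The stratification variable appears there only as an example.

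Other sections state other rules. Aim 2 uses baseline significance alone: "Demographic measures and other characteristics that are significantly different between the two treatment groups at baseline, will be included as covariates". Section 5.8.4 item 2 admits variables that are either unbalanced or predictive of outcome.

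**The concern.** The SAP describes stratified, blocked randomization. Differences between BA-PEP and SC at baseline are therefore chance, and a significance test of them says nothing about which variables predict goal attainment. A strong predictor that happens to be balanced is dropped at the first step, although adjusting for it would sharpen the comparison.

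The second step uses outcome data. Together with the open list in Aim 1 and the unnamed BDI scoring, this means two analysts could both follow the SAP and report different primary odds ratios. What is at stake is that the primary estimate is defined only after outcomes are known, plus some power at the smaller effects the SAP says it can detect.

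**Working it through.** **Inputs from the SAP.** 70 patients per arm (50 fatigued and 20 not); expected rates 60% vs 25%; a 23-point difference such as 48% vs 25% said to be detectable with 80% power. Two-sided 5% is stated only for Hypothesis 2 and is assumed here for Hypothesis 1.

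**The SAP's power figures.** Power = Φ[(d − 1.96·SE0)/SE1], with SE0 from the pooled rate and SE1 from the separate rates.
- 60% vs 25%: SE0 = √(2×0.425×0.575/70) = 0.0836; SE1 = √((0.24+0.1875)/70) = 0.0781; (0.35 − 0.1638)/0.0781 = 2.38, so power is 99.1% (SAP: over 95%).
- 48% vs 25%: SE0 = 0.0814; SE1 = 0.0790; (0.23 − 0.1595)/0.0790 = 0.89, so power is 81.4% (SAP: 80%).

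Both agree with the SAP.

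**How often chance triggers step one.** With k independent tests at an assumed 5% level, the chance of at least one significant difference is 1 − 0.95^k: 40.1% for k = 10 and 64.2% for k = 20. The SAP does not give k. Correlated variables would lower these figures.

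**Simulation of the whole rule.** Logistic model with Wald tests and 140 patients; stratum and BDI always included; marginal rates calibrated to the SAP's percentages. Assumed: BDI odds ratio 1.5 per SD; independent normal covariates; both selection steps at p<.05; three candidates prognostic at an odds ratio of 1.0, 1.5 or 2.0 per SD (1.0 means no prognostic value). 10,000 trials per setting with 10 candidates, 5,000 with 20.

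Power (%) with 10 candidates, by prognostic odds ratio 1.0 / 1.5 / 2.0:

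| Model | 48% vs 25% | 60% vs 25% |
|---|---|---|
| Stratum + BDI only | 83.2 / 82.9 / 81.7 | 99.3 / 99.1 / 99.2 |
| Note #1 rule | 82.8 / 82.4 / 82.0 | 99.2 / 99.1 / 99.3 |
| Stratum + BDI + three fixed predictors | 82.9 / 86.0 / 89.3 | 99.2 / 99.4 / 99.8 |
| Same, one predictor with three levels | 82.8 / 85.9 / 88.7 | 99.2 / 99.3 / 99.7 |

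- *A covariate enters under Note #1:* 4.0 / 9.8 / 14.0% of trials at 48% vs 25%, and 6.0 / 10.3 / 14.3% at 60% vs 25%. With 20 candidates the range is 8-20%.
- *Shift in the odds ratio when one enters:* median factor 1.12 / 1.14 / 1.19 at 48% vs 25% and 1.09 / 1.10 / 1.12 at 60% vs 25%; 90th percentile 1.15 to 1.60. Part of this is the change from a marginal to a conditional odds ratio.
- *No prognostic covariate enters (odds ratio 1.5-2.0):* 88-93% of trials, or 88-94% with 20 candidates.
- *Significance decision differs from stratum + BDI:* 0.1% of trials at 60% vs 25%; 0.5 / 1.5 / 2.2% at 48% vs 25%.
- *Type I error (25% or 40% in both arms):* stratum + BDI 4.9-5.2%; Note #1 4.7-5.0%; fixed lists 5.2-5.6%.
- *20 candidates, 48% vs 25%:* Note #1 82.9 / 81.6 / 82.0%; three fixed predictors 83.3 / 85.1 / 89.4%.

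Simulation error with 10,000 trials is about 0.2 points near 5% and 0.4 points near 83%.

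A separate simulation used 15 candidates, three of them prognostic with a log odds ratio of 0.7 per SD, and matched 48% vs 25% on the conditional scale. Power was about 63% under Note #1 and 72% with the three fixed, with type I error 4.5% under Note #1. The direction agrees; the levels are not comparable because the calibration differs.

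**The case against.** The strongest reply is that little harm is shown. Run mechanically, the rule does not inflate type I error. Even reporting the smaller of the stratum + BDI and Note #1 p-values gave only 5.3%. At the planned 60% vs 25% the conclusion almost never changes. All of this stands.

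Nor does deleting the screen gain power by itself: stratum + BDI and Note #1 differ by at most 0.5 points at 48% vs 25%. The gain comes entirely from adding predictors that prove prognostic, and the SAP gives no prognostic strengths. This also stands, so the power gain is conditional and is not the main argument.

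It can be said that a variable both imbalanced and related to outcome is one where chance can distort the observed comparison. That supports a sensitivity analysis. It does not support letting such variables redefine the primary estimate. Nor does a fixed list leave the odds ratio where it was: prognostic covariates move it from marginal to conditional in every trial. The difference is that the target is then known beforehand.

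Finally, Note #1 might be called a prespecified rule. As written it cannot be executed without further choices, because it has no list, test, level or outcome criterion. The protocol may list the measures, but that would not make the stated selection method sound.

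**Conclusion.** The concern holds. The SAP states an unsound selection rule and applies it to the primary comparison, whose covariate list is also left open. The change should be made, although the numerical effect is modest: in most trials the rule adds nothing and the model is stratum + BDI.

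The case for prespecification rests on the text alone. The sizes rest on the assumed number of candidates, their independence, the 5% screening level and the assumed prognostic strengths. The simulation keeps one BDI scoring and always includes the stratum, so it does not measure the effect of leaving those choices open.

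The differing rules in Aim 2 and 5.8.4 item 2 also need reconciling with Note #1, but they do not reach the primary analysis.

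**What to change.** For the randomized BA-PEP vs SC comparisons:

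1. Delete the significance screen in Note #1 and state one closed covariate list before outcomes are seen: fatigue stratum; baseline BDI, naming standard or prorated scoring; and a small set of baseline predictors. Hypothesis 3 offers candidates: "We expect several of these characteristics particularly depression, age, health status and neuropsychological function, to show significant association to successful goal attainment". One choice is age, one named health-status measure and one named neuropsychological summary.
2. Write that list into the Aim 1 model, removing the open wording, and refer Aim 2 and 5.8.4 item 2 to it.
3. Report baseline tables descriptively, and put any adjustment for observed imbalance in a labelled sensitivity analysis.
4. Exempt the historical-control analyses in 5.8.4 item 1 ("The historical Control data will be added to all analyses described above"). They are not randomized, so baseline comparison and adjustment remain necessary there.

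If no further predictors are wanted, a closed list of stratum and BDI also fixes the odds ratio, without the possible power gain.

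The cost is wording in Note #1, Aims 1 and 2 and 5.8.4 item 2, plus an early decision on about three measures that Aim 3 already plans to use. The downside is about three more degrees of freedom and no later additions to the primary model. Expected successes are 70 × (0.60 + 0.25) = 59.5, or 70 × (0.48 + 0.25) = 51.1. Over six terms (treatment, stratum, BDI and three predictors) that is 9.9 or 8.5 per term; over seven, with a three-level health-status category, 8.5 or 7.3.

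### Aim 2: baseline covariates entered without a time interaction leave the deciding treatment-by-time test essentially unadjusted

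*SAP*

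**What the plan says.** The Aim 2 analysis plan in SAP 5.8.3 specifies a longitudinal mixed model "with main effect of time, treatment and interaction between treatment and time effect". Baseline is part of the outcome vector: "The within subjects repeated measure across time will be the baseline session, session 4, and session 8 [end of treatment] assessments".

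On adjustment, the same paragraph says "Demographic measures and other characteristics that are significantly different between the two treatment groups at baseline, will be included as covariates". Separately, Note #1 in section 5.8 says "a depression measure (BDI [67]) will be used as a covariate in all analyses". Note #1 does not say whether this is the baseline or a concurrent BDI score; the baseline score is named only under Aim 3.

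On the deciding test, the plan says "The main focus of the analysis will be on the interaction term of treatment and time, which addresses treatment group response over time". A follow-up test depends on it: "If the interaction term of treatment and time is found to be significant, we will test the contrast between treatment groups at session 8".

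Patients with incomplete data stay in the model, according to the Missing Data paragraph: "In the presence of missing data, Mixed Models uses all data, estimates parameters and test hypotheses about them but do not impute missing values".

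No covariate-by-time term appears in the Aim 2 paragraph or in Note #1.

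**The concern.** Treatment-by-time compares the arm difference at one visit with the arm difference at another. A time-constant covariate entered as a main effect shifts all three of a patient's values by the same amount. It therefore shifts the arm difference equally at every visit and drops out of the comparison between visits. To adjust the interaction, the covariate's effect must be allowed to differ by visit.

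The plan has chosen to correct observed baseline imbalance, and a reader will take Hypothesis 2 to be corrected in that way. If an imbalanced factor also predicts how much patients improve, its contribution stays in the estimate that decides the hypothesis. Any precision the covariate could bring to that estimate is also lost.

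**Working it through.** **Inputs from the SAP.** 70 patients per arm, three visits, correlation between repeated measures .30, two-sided alpha .05, and a Hypothesis 2 effect size of .45 at 80% power (Power Considerations).

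**The plan's own figure.** A session 8 comparison adjusted for baseline has residual SD sqrt(1 − 0.30²) = 0.954. With 70 per arm it gives power 79.7%, 84.5%, 89.7% and 94.9% for effects .45, .48, .52 and .58, against the stated 80, 85, 90 and 95%. The figures reproduce. Below, .45 serves only as a yardstick, taken to be in single-visit SD units; the SAP does not define the unit.

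**Algebra, complete data.** With covariate X and coefficient b, the adjusted arm difference at visit t is

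(mean of arm 1 at t − mean of arm 0 at t) − b × (mean X in arm 1 − mean X in arm 0).

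The second term does not depend on t. Subtracting the baseline difference from the session 8 difference removes it, whatever b and the imbalance are.

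**Simulation.** 100 trials per scenario, random-intercept model fitted by REML, categorical visit. Assumed, not from the SAP: imbalance 0.4 SD, covariate effect 0.5, true session 8 interaction 0.45, about 25% dropout depending on the covariate where dropout is used.

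| Scenario | Estimate | No covariate | Main effect | Covariate-by-time |
|---|---|---|---|---|
| Complete data, covariate does not affect change | Interaction (SE) | 0.424 (0.184) | 0.424 (0.184) | 0.423 (0.189) |
| Same | Session 8 contrast (SE) | 0.622 (0.171) | 0.419 (0.152) | 0.417 (0.154) |
| Complete data, covariate affects change by 0.3 per SD | Interaction | 0.546 | 0.546 | 0.423 |
| Dropout, covariate does not affect change | Interaction (SE) | 0.419 (0.205) | 0.434 (0.203) | 0.437 (0.208) |
| Dropout, covariate affects change by 0.3 per SD | Interaction | 0.526 | 0.542 | 0.437 |

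- With complete data, the interaction estimates with and without the main effect differ by at most about 1e-14 in any trial. One trial fitted with unstructured covariance agrees: 0.414 (SE 0.176) both ways.
- The expected slope bias is 0.3 × 0.4 = 0.12. The main effect removes none of it (0.546 to 0.546); covariate-by-time removes it (0.546 − 0.423 = 0.123). The Monte Carlo error of each mean is about 0.19/sqrt(100) = 0.019, so 0.423 is compatible with 0.45.
- With dropout and no slope effect, the main effect moves the interaction by 0.027 on average and 0.11 at most.
- The session 8 contrast does move, by about the expected 0.5 × 0.4 = 0.20.

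**Size at a just-significant imbalance.** The difference giving p = .05 at 70 per arm is 1.977 × sqrt(2/70) = 0.334 SD. The SD of baseline-to-session-8 change is sqrt(2 × (1 − 0.30)) = sqrt(1.4) = 1.183, and the SE of the arm difference in change is sqrt(1.4 × 2/70) = 0.20. For an assumed correlation r between the factor and change:

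- Bias = 0.334 × r × 1.183.
- Conditional type I error, 1 df = Φ(−1.96 + bias/0.20) + Φ(−1.96 − bias/0.20).
- For the 2-df interaction with an effect growing linearly over visits, the noncentrality is (bias/0.20)².
- Net variance reduction from covariate-by-time = 1 − (1 − r²)(1 + 0.334²/4). The last factor is the price of adjusting for an imbalanced covariate.

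| r | Bias (SD) | Share of .45 | Type I, 1 df | Type I, 2 df | Net variance reduction |
|---|---|---|---|---|---|
| .2 | 0.079 | 18% | 6.8% | 6.2% | 1% |
| .3 | 0.119 | 26% | 9.1% | 7.7% | 6% |
| .4 | 0.158 | 35% | 12.4% | 10.0% | 14% |

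**The case against.** Four points against the concern have force.

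- A reader might infer that the planned adjustment does nothing. It does not follow. The session 8 contrast is a planned test, and in the simulation a main effect moves it from 0.622 to 0.419 and lowers its SE from 0.171 to 0.152. What remains is that this contrast is run only after a significant interaction, so the test that opens the gate is the essentially unadjusted one.
- A reader might infer that the interaction is exactly unchanged in the trial's real data. Exact equality needs complete data and a time-constant covariate, and the SAP keeps incomplete patients. With covariate-related dropout the term moves slightly, but too little to count as adjustment.
- The BDI may not be a baseline value. Note #1 leaves its time point open. In the simulation with complete data and no slope effect, a concurrent BDI moves the interaction from 0.424 to 0.563, so it is not inert. A concurrent score is, however, measured after randomization, which is a problem of another kind. Either way the time point needs stating.
- Entering variables as covariates does not rule out time interactions. Main effects are the natural reading, since the paragraph names treatment-by-time and no other interaction, but the text does not say so outright.

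A reader might also take 7 to 12% as the error rate of the planned test. It is not. It holds only given an imbalance of the assumed size in a factor that predicts change, and for a single-degree-of-freedom contrast. Over all randomizations the interaction test keeps its 5%.

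**Conclusion.** The concern holds in a limited form. The SAP's stated correction for imbalance does not reach the term that decides Hypothesis 2, if covariates enter as main effects of baseline values. The cancellation is exact with complete data and close to exact with dropout. The bias and conditional error figures rest on an assumed 0.33 SD imbalance and assumed correlations of .2 to .4 with change, neither of which the SAP gives. Smaller imbalances or weaker correlations make the issue smaller.

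This is a cheap improvement to a secondary analysis, not an invalid test. The Aim 1 logistic regression is unaffected.

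**What to change.** In the Aim 2 analysis paragraph, state that baseline covariates, including the baseline BDI score, enter the model together with their interaction with time, with visit as a categorical factor. This also settles the BDI time point for Aim 2.

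The cost is one SAP sentence, one extra model term per covariate, and two degrees of freedom per continuous or binary covariate. The net precision gain is small when the covariate is only weakly related to change: about 1% of variance at r = .2 and the 0.334 SD imbalance. In the simulated case where the covariate did not affect change, the interaction SE rose slightly, from 0.184 to 0.189.
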